### **5.5 Treatments**

#### **5.5.1 Treatments Administered**

During the randomized double-blind Induction Study, subjects assigned to the higher induction regimen will receive blinded adalimumab 160 mg (4 syringes) at Baseline, Week 1, Week 2, and Week 3. At Week 4, subjects will receive 40 mg (1 syringe) eow through Week 12.

Subjects assigned to the standard induction regimen will receive blinded adalimumab 160 mg (4 syringes) at Baseline and matching placebo (4 syringes) at Week 1. Subjects will receive 80 mg (2 syringes) and placebo (2 syringes) at Week 2 and matching placebo (4 syringes) at Week 3. At Week 4, subjects will receive 40 mg (1 syringe) eow through Week 12.

At Week 12, subjects will be re-randomized in a 1:1 ratio to one of the two double-blinded exploratory treatment regimens (adalimumab clinically adjusted [CA] regimen and adalimumab therapeutic drug monitoring [TDM] regimen). The re-randomization at Week 12 will be stratified by induction treatment regimen, clinical response (CR-70)

status at Week 12 and decrease in SES-CD > 50% from Baseline per the site investigator reading at Week 12. Among subjects achieving SES-CD > 50% from Baseline at Week 12, the randomization will be further stratified by achievement of an SES-CD  $\leq$  4 and at least a 2 point reduction versus baseline and no subscore greater than 1 in any individual variable using the Week 12 SES-CD value provided by the site.

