## **5.6 Discussion and Justification of Study Design**

### **5.6.1 Discussion of Study Design and Choice of Control Groups**

The design of this clinical trial was chosen to demonstrate the efficacy of a higher induction regimen of adalimumab compared to the standard induction regimen. The efficacy time points of Week 4 and Week 12 are comparable to prior studies with adalimumab, specifically Study M02-403, Study M04-691, and Study M05-769. The

study is double-blinded and subjects are randomized to receive a higher induction regimen of adalimumab or a standard induction regimen of adalimumab. After the induction regimens are provided, subjects in both treatment groups will receive blinded adalimumab 40 mg eow until Week 12. Subjects will begin tapering of corticosteroids at Week 4.

No placebo arm is planned since there is well-documented efficacy of adalimumab in CD and because the purpose of this study is to achieve better efficacy than the standard induction regimen in terms of clinical remission and endoscopic improvement. Additionally, since subjects will be required to have failed or been intolerant of standard therapies and have evidence of endoscopic damage confirmed by a central reader, it would be not medically acceptable to deny those patients effective treatment or feasible to enroll patients in the trial when adalimumab is available to be prescribed for CD.

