### **8.1.4.2 Secondary Efficacy Variables for Induction Study**

Secondary efficacy variables are divided into two groups. The first group includes ranked secondary endpoints, which are ranked by clinical importance. Statistical significance is assessed at 0.050 (2-sided) in ranked endpoint order until the significant level exceeds

0.05. No additional statistically significant treatment differences could be declared after the first ranked endpoint fails to achieve 0.05. The second group includes all other additional secondary variables.

For categorical ranked and non-ranked secondary endpoints, the difference in proportions of subjects between treatment groups will be analyzed using the CMH test adjusted for stratification variables. Additionally, the two-sided 95% confidence interval for the difference in proportions will be provided. The non-responder imputation will be used for subjects with missing data at the endpoint evaluated. The last observation carried forward (LOCF) method will also be used as the sensitivity analyses for the primary and ranked secondary endpoints.

Change from Baseline in continuous ranked and non-ranked secondary endpoints will be analyzed using an ANCOVA model including factors of treatment and adjusting for the baseline values and the stratification variables. For analyses of changes from Baseline variables, both LOCF and OC analyses will be performed. The LOCF analysis is considered primary for inferential purposes. In addition, Mixed-Effect Model Repeated Measure (MMRM) will be applied, wherever appropriate, as a sensitivity analysis for the longitudinal continuous endpoints.

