Subjects in whom the CD-related corticosteroids (systemic or rectal corticosteroids) that were not being taken at Baseline and are initiated during the study or who have equivalent dose of these medications increased to greater than the dose taken at Baseline will be censored for efficacy assessments (i.e., will be considered non-responders for categorical endpoints and will have last non-missing values carried forward for non-categorical assessments) from that point through the end of the study. These subjects will continue to be evaluated in the safety population.

The equivalent steroid dose will be determined based on the table below:

Corticosteroid	Equivalent Dose (mg)
Cortisone	25
Hydrocortisone	20
Prednisone	5
Prednisolone	5
Triamcinolone	4.0
Methylprednisolone	4.0
Betamethasone	0.75
Dexamethasone	0.75
Budesonide	1
Beclomethasone	5
Beclometasone	5

Definition of Missing Data Imputation

The following imputation methods will be used to impute missing values in the efficacy analyses. In addition, an observed case analysis will be performed.

Non-Responder Imputation (NRI)

The NRI approach is used for binary efficacy variables. These variables can take values of 'Achieved' or 'Not Achieved' or may be missing for any reason including discontinuation from study. According to the NRI imputation approach, all missing values will be considered as 'Not Achieved.'

Last Observation Carried Forward (LOCF)

For all variables (categorical variables and continuous variables), the following rules will be used for the LOCF approach:

1. Baseline and Pre-Baseline values will not be used to impute the missing Post-Baseline values.

2. Missing values after Study Day 1 will be imputed using the latest non-missing values after Day 1 and prior to the missing value. If there are no non-missing values after Baseline, then the LOCF value will be missing.

Mixed-Effect Model Repeated Measure (MMRM)

The MMRM model will be used for continuous efficacy variables with longitudinal data as a sensitivity analysis. The MMRM model includes the baseline values as covariate; randomization strata, region (US versus non-US), treatment, time point and treatment-by-time point interaction as fixed effects; and subjects within treatment as random effect. An unstructured (co)variance structure will be used to model the within-subject error. The comparison at a time point will be the contrast between treatments at that time point.

Observed Case (OC)

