Both LOCF and OC analyses will be performed for continuous endpoints. The LOCF analysis is considered primary for inferential purposes. In addition, Mixed-Effect Model Repeated Measure (MMRM) will be applied as a sensitivity analysis, wherever appropriate, for the longitudinal continuous endpoints.

For endoscopy related endpoints, there will be no LOCF imputation as there is only one post-baseline endoscopy during Induction. Only OC will be used as a sensitivity analysis.

The difference in proportions of subjects between treatment groups will be analyzed using the two-sided Cochran-Mantel-Haenszel (CMH) test adjusted for hs-CRP at Baseline (< 10 and ≥ 10 mg/L), prior infliximab use (or prior anti-TNF use for subjects randomized under original protocol), and Crohn's disease severity (CDAI ≤ 300 , > 300) at Baseline. Additionally, the CMH-based two-sided 95% confidence interval (CI) for the difference in the proportions between the treatment groups will be calculated. An exact CMH test will be used to handle zero cells.

The difference in change from Baseline between treatment groups will be analyzed using an ANCOVA model including factors of treatment, hs-CRP at Baseline, prior infliximab use (or prior anti-TNF use for subjects randomized under original protocol), and Crohn's disease severity at Baseline, and Baseline values. Parameter estimates with 95% confidence interval and *P*-value will be provided.

All additional efficacy endpoints will be non-ranked.

- Proportion of subjects with clinical response (decrease CDAI ≥ 70 points from Baseline) at each scheduled visit in Induction Study.

- Proportion of subjects with enhanced clinical response (decrease CDAI ≥ 100 points from Baseline) at each scheduled visit in Induction Study.
- Proportion of subjects who discontinue corticosteroid use at each scheduled visit in Induction Study among subject taking corticosteroids at Baseline.
- Proportion of subjects who achieve a composite subtotal score of SFPS < 50 at Week 12 who had an SFPS ≥ 100 at Baseline.
- Proportion of subjects who achieve a composite subtotal score of SFPS < 50 at Week 4 who had an SFPS ≥ 100 at Baseline.
- Proportion of subjects who achieve SES-CD ≤ 3 and at least a 2 point reduction versus baseline and no subscore greater than 1 in any individual variable at Week 12.
- Proportion of subjects with SES-CD = 0 at Week 12.
- Change from Baseline in fecal calprotectin level at each scheduled visit in Induction Study.

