- Change from Baseline in hs-CRP at each scheduled visit in Induction Study.
- Change in IBDQ total score and individual IBDQ domain scores (bowel, emotional, social, systemic) from Baseline at each scheduled visit in Induction Study.
- Proportion of subjects with Inflammatory Bowel Disease Questionnaire (IBDQ) response (increase ≥ 16 points from Baseline) at each scheduled visit in Induction Study.
- Proportion of subjects with IBDQ remission (IBDQ ≥ 170 points) at each scheduled visit in Induction Study.
- Proportion of subjects achieving response in IBDQ fatigue item (increase of IBDQ fatigue item score ≥ 1) at Week 4
- Change in WPAI from Baseline at each scheduled visit in Induction Study.
- Change in EQ-5D from Baseline at each scheduled visit in Induction Study.
- Change in CDAI from Baseline at each scheduled visit in Induction Study.
- Change in SFPS from Baseline at each scheduled visit in Induction Study.
- Change in Abdominal Pain Rating Scale score from Baseline at each scheduled visit in Induction Study.

- Change in Bristol Stool Chart score from Baseline at each scheduled visit in Induction Study.
- Proportion of subjects who achieve Bristol Stool Chart response at each scheduled visit in Induction Study.
- Proportion of subjects who achieve CDAI remission (CDAI < 150) at each visit in Induction Study.
- Proportion of subjects who achieve SFPS remission (SFPS < 50) at each scheduled visit in Induction Study.
- Change in each CDAI component subscore (number of liquid or very soft stools, abdominal pain rating, general well-being, CD related complications, anti-diarrhea use, abdominal mass, hematocrit, body weight) from Baseline at each scheduled visit in Induction Study.
- Time to clinical remission (CDAI < 150) in Induction Study.
- Time to clinical response (CR –70) in Induction Study.
- Time to all cause Hospitalization in Induction Study.
- Time to CD-related Hospitalization in Induction Study.
- Proportion of subjects with no draining fistulas at Week 12 among subjects with draining fistula at Baseline.
- Proportion of subjects in each treatment group with > 50% reduction from Baseline in the number of draining fistulas at Week 12 among subjects with draining fistula at Baseline.
- Resolution of extra-intestinal manifestations over time at each scheduled visit in Induction Study.
- Proportion of subjects with an SES-CD decrease of ≥ 3 points compared to Baseline at Week 12.

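### LOCF is the inferential analysis for the non-ranked repeated continuous Induction endpoints; if an early benefit of the higher regimen fades, dropouts carry it into the Week 12 comparison, and the planned MMRM would be the better choice

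*Protocol*

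**What the plan says.** Protocol 8.1.4.2 analyses change from Baseline by ANCOVA, with both LOCF and observed-case (OC) versions, and settles which one carries the inference: "The LOCF analysis is considered primary for inferential purposes". On the alternative it says "Mixed-Effect Model Repeated Measure (MMRM) will be applied, wherever appropriate, as a sensitivity analysis for the longitudinal continuous endpoints". The synopsis and Induction SAP 10.3 say the same; the SAP adds "Both LOCF and OC analyses will be performed for continuous endpoints".

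Induction SAP 6.0 defines the carrying rule: "Missing values after Study Day 1 will be imputed using the latest non-missing values after Day 1 and prior to the missing value". It also limits it: "Baseline and Pre-Baseline values will not be used to impute the missing Post-Baseline values". So only post-Baseline values are carried.

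On dosing, protocol 5.5.1 gives the higher arm 160 mg at Baseline and Weeks 1, 2 and 3. The standard arm gets 160 mg, placebo, 80 mg and placebo. Then, for both arms, "At Week 4, subjects will receive 40 mg (1 syringe) eow through Week 12". Section 5.6.1 confirms it: "After the induction regimens are provided, subjects in both treatment groups will receive blinded adalimumab 40 mg eow until Week 12".

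The exposed endpoints are the repeated continuous ones in Induction SAP 10.3, for example "Change in CDAI from Baseline at each scheduled visit in Induction Study", with the corresponding changes in SFPS, IBDQ, hs-CRP, EQ-5D, WPAI, abdominal pain rating and Bristol Stool Chart score. All are non-ranked. Each receives an estimate, a 95% confidence interval and a p-value.

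**The concern.** A Week 12 comparison of these measures asks whether more intensive dosing in the first weeks still shows after both arms have shared one dose for eight weeks. For a subject who leaves between Week 4 and Week 12, LOCF answers with a value taken at or soon after the period when the doses differed.

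The sponsor plans on a large early contrast: protocol 8.2 assumes 50% against 30% in clinical remission at Week 4. If a contrast of that kind also exists on the continuous scales and then shrinks, each dropout contributes the larger, earlier difference as a Week 12 result. The imputed value is also analysed as if observed. At stake are the Week 12 estimates, intervals and p-values for a set of symptom, biomarker and quality-of-life measures. The study's confirmatory conclusion is not at stake.

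**Working it through.** **1. The plan's own figure.** The documents give no figure for LOCF or dropout, so the nearest one to reproduce is the power statement in protocol 8.2. Exact enumeration of Fisher's test with 300 and 200 subjects at two-sided 0.05 gives 99.4% for 50% against 30%, and 99.8% for 66% against 44%. The product is 0.994 × 0.998 = 99.2%. All agree with the stated 99%, about 99% and more than 98%.

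**2. Inputs for the LOCF check.**
- From the documents: 300 and 200 subjects; two-sided 0.05; the same dose from Week 4; LOCF carrying post-Baseline values only.
- Assumed: true Week 12 difference of zero; a share d of 5% to 20% of each arm leaving after Week 4; an early difference δ of 0.25 or 0.524 SD. The larger δ is the planned 50% against 30% on a probit scale: Φ⁻¹(0.50) − Φ⁻¹(0.30) = 0.524.

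**3. Closed form.** The false Week 12 difference is d × δ. The standard error is √(1/300 + 1/200) = 0.0913 SD. With k = dδ/0.0913, the two-sided rejection rate is Φ(−1.96 − k) + 1 − Φ(1.96 − k).

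| Dropout d | Bias, δ = 0.25 | Rejection | Bias, δ = 0.524 | Rejection |
|---|---|---|---|---|
| 5% | 0.013 SD | 5.2% | 0.026 SD | 6.0% |
| 10% | 0.025 SD | 5.9% | 0.052 SD | 8.9% |
| 15% | 0.038 SD | 7.0% | 0.079 SD | 13.8% |
| 20% | 0.050 SD | 8.5% | 0.105 SD | 21.0% |

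Example: d = 0.20 and δ = 0.524 give k = 0.1049/0.0913 = 1.149 and a rejection rate of 21.0%.

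**4. Simulation.** There were 3,000 trials per setting, five visits (Weeks 2, 4, 6, 8 and 12), an assumed between-visit correlation of 0.6, a Week 4 difference of 0.524 SD and a true Week 12 difference of zero. The difference either waned steadily to zero or stayed flat to Week 8 and then vanished. Dropout was either random or more likely after a poor last value. Negative bias favours the higher regimen.

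| Time course | Dropout | LOCF bias (SD) | LOCF rejection | MMRM-type bias (SD) | MMRM-type rejection |
|---|---|---|---|---|---|
| Wanes | random, 10% | −0.038 | 7.3% | 0.000 | 5.8% |
| Wanes | random, 20% | −0.077 | 12.9% | −0.002 | 4.9% |
| Wanes | by last value, lower | −0.042 | 7.0% | −0.001 | 5.2% |
| Wanes | by last value, higher | −0.081 | 13.5% | −0.001 | 4.8% |
| Flat, then zero | random, 10% | −0.054 | 9.3% | −0.003 | 5.0% |
| Flat, then zero | random, 20% | −0.099 | 19.6% | 0.000 | 5.0% |
| Flat, then zero | by last value, lower | −0.051 | 8.1% | −0.001 | 5.3% |
| Flat, then zero | by last value, higher | −0.095 | 17.5% | −0.001 | 4.6% |

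In the lower setting about 4% to 5% of the higher arm and 8% of the standard arm leave; in the higher setting about 9% to 10% and 16%. The MMRM-type estimate is maximum likelihood under monotone missingness. Its rejection rate uses the simulated standard deviation of the estimate, so it shows absence of bias and does not test the model's own standard error.

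**5. Two controls.** With no benefit at any visit, LOCF rejects about 5% of the time (4.8% to 5.3%), so the inflation comes from the fading early difference. In the two settings above where dropout follows the last value, OC is biased the other way, by +0.025 to +0.055 SD, and rejects 6.0% to 8.8%.

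**6. Reach.** The co-primary and categorical ranked endpoints use non-responder imputation (Induction SAP 10.2 and 10.3). The only ranked continuous endpoint is number 6, change in fecal calprotectin at Week 4. Its first scheduled post-Baseline sample is at Week 4, and Induction SAP Table 6 assigns Days 2 to 57 to that visit, so nothing earlier exists to carry.

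**The case against.** The case for leaving the plan alone has several parts.

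- **No controlled claim rests on these p-values.** The endpoints lie outside the testing hierarchy. This stands, and it limits the point to a cheap improvement.
- **The direction is not known in advance.** A reader might infer that LOCF here always favours the higher regimen and that its intervals are always too optimistic. The documents do not support that. They give no time course for these measures, and the planning assumption for endoscopy is a Week 12 advantage of 66% against 44%, not a vanished one. If benefit grows after Week 8, the bias can reverse; with no early benefit there is none.
- **The size is assumed.** At 5% dropout the inflation is about one percentage point or less. Protocol 5.4.1 also asks for a discontinuation visit within 2 weeks of the last dose, and the SAP maps such visits into its windows. LOCF will therefore often carry the value at withdrawal, which the simulation did not model. That value still precedes Week 12 for anyone who leaves early.
- **OC and MMRM are already planned**, so a discrepancy would be visible. True, but the plan says which result governs, and OC is not a clean check.
- **The planned MMRM is not ready as written.** This also stands. SAP 6.0 combines a subject random effect with an unstructured within-subject covariance, which is redundant. Values after steroid censoring are replaced by the last value, even in OC, and the SAP does not say whether MMRM uses the replaced values.

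**Conclusion.** The point holds for the non-ranked repeated continuous endpoints. LOCF is the weaker choice for a design in which the doses differ early and then coincide, and a better method is already in the SAP. Over assumed dropout of 5% to 20% and an early difference of 0.25 to 0.52 SD that is gone by Week 12, a nominal 5% test rejects about 5% to 21% of the time. In the simulated settings, run at the 0.52 SD difference, an MMRM-type estimate has bias of at most 0.003 SD and rejects 4.6% to 5.8% of the time.

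These figures rest on a dropout rate, an early difference, a time course and a correlation that the documents do not supply. They show what can happen, not what is expected. A reader might also infer that the study's Week 12 conclusion is in doubt. It is not: the confirmatory Week 12 results come from non-responder imputation, and ranked endpoint 6 is measured at Week 4 with nothing earlier to carry.

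**What to change.** Before the Week 12 unblinding:

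- In the synopsis, protocol 8.1.4.2 and Induction SAP 10.3, name MMRM as the inferential analysis for the non-ranked continuous endpoints measured at repeated Induction visits (change in CDAI, SFPS, IBDQ, hs-CRP, EQ-5D, WPAI, abdominal pain and Bristol score). Keep LOCF with ANCOVA as supportive.
- In Induction SAP 6.0, drop the subject random effect when the unstructured covariance is used.
- In the same section, state how values after steroid censoring enter the MMRM. If they enter as carried-forward values, part of the problem returns.
- Leave ranked endpoint 6 (fecal calprotectin at Week 4) as it is.

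The cost is wording and some specification work. It needs no new data and no change in sample size. The documents show that MMRM is planned, but not that it has been programmed. The downside is that MMRM relies on missing at random; the LOCF table remains as a comparison. Settling the choice beforehand avoids picking between discordant LOCF and MMRM results after they are seen.

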#### **8.1.4.3 Efficacy Variables for Maintenance Study**

For categorical endpoints, the difference in proportions of subjects between treatment groups will be analyzed using the CMH test adjusted for stratification variables. Additionally, the two-sided 95% confidence interval for the difference in proportions will be provided. The non-responder imputation will be used for subjects with missing data at the endpoint evaluated. The last observation carried forward (LOCF) method will also be used as the sensitivity analyses for the primary and ranked secondary endpoints.

Change from Baseline in continuous ranked and non-ranked secondary endpoints will be analyzed using an ANCOVA model including factors of treatment and adjusting for the baseline values and the stratification variables. For analyses of changes from Baseline

variables, both LOCF and OC analyses will be performed. The LOCF analysis is considered primary for inferential purposes. In addition, Mixed-Effect Model Repeated Measure (MMRM) will be applied, wherever appropriate, as a sensitivity analysis for the longitudinal continuous endpoints.

### **8.1.5 Statistical Analyses of Safety**

Adverse events (AEs), laboratory data and vital signs are the primary safety parameters in this study. All safety comparisons will be performed for both induction and maintenance periods between treatment groups using the safety analysis set.

Treatment-emergent AEs are defined as events that begin or worsen either on or after the first dose of the study drug and within 70 days after the last dose of the study drug for subjects who do not participate in the OLE or until first dose of study drug in the OLE study if the subject is a completer and is enrolled in the OLE.

Treatment-emergent AEs will be summarized separately for: a) Baseline to Week 12; b) Week 12 to Week 56; c) Baseline to Week 56 (overall study duration). An overview of treatment-emergent AEs, including AEs of special interest such as adverse events leading to death and adverse events leading to premature discontinuation (see details in the SAP), AEs by Medical Dictionary for Drug Regulatory Activities (MedDRA version 20.1 or later) preferred term and system organ class, AEs by maximum relationship to study drug, and AEs by maximum severity will be summarized by number and percentage.

Changes in laboratory data will be described using statistical characteristics and compared between treatment groups will be performed using a one-way Analysis of Variance (ANOVA). In addition, shift tables and listings will be provided for abnormal values, whereby the normal range of the analyzing laboratory will be used. Vital signs will be analyzed similarly.

